| Sponsor | The sponsor is the party that commissions the organization or performance of the research, for example a pharmaceutical company, academic hospital, scientific organization or investigator. A party that provides funding for a study, but does not commission it, is not regarded as the sponsor, but referred to as a subsidizing party. |
| SF36 | short form 36 questionnaire |
| SUSAR | suspected unexpected serious adverse reaction |
| TBW | total body water |
| Tx | transplantation |

SUMMARY

Rationale: Preservation of residual renal function is independently associated with reduced mortality and improved outcomes in patients with end stage renal disease. Fluid status and blood pressure influence the rate of kidney function decline early in the course of chronic kidney disease (CKD). The technique of bioimpedance spectroscopy (BIS) can offer valuable information on fluid dynamics and body composition, in addition to standard care.

Objectives: This study aims to investigate the role of thoracic and whole body BIS in the hemodynamic profile of patients with CKD. The primary objective is to associate the BIS-determined fluid status [fluid overload (FO) versus non-FO] with kidney function decline in patients with CKD stage 3 (CKD-EPI 59-30ml/min), 4 (CKD-EPI 29-15ml/min) and 5 (CKD-EPI < 15 ml/min). The secondary objective is to identify the clinical factors associated with FO during a longitudinal follow up. Secondary outcomes of interest are the central volume status (measured by echocardiography and thoracic BIS in combination with photoplethysmography), the cardiac systolic and diastolic function, CV events, hospitalizations, inflammatory- and nutrition status, and quality of life, between CKD stages 3, 4 and 5 and compare them to an age- and sex- matched healthy control group.

Study design: An non-randomized intervention study with a longitudinal follow up of the cohort and some cross-sectional analysis.

Study population: Prevalent CKD patients stage 3 - 5 not on dialysis and an age- and sex- matched healthy control group, will be included during a period of 18 months and prospectively followed up over a period of 12 months.

Intervention: During each study visit BIS- and blood pressure measurements will be performed, and blood- and urine samples will be taken in each subject.

Main study parameters/endpoints:

- Whole body fluid status, measured by whole body BIS
- Central volume status, measured by thoracic BIS, photoplethysmography and echocardiography
- Blood pressure, measured by automatic oscillometric device
- Determinants of BIS signal in CKD population: gender, comorbidities
- Rate of kidney function decline, determined by eGFR CKD-EPI, mixed urea and creatinine clearance, and urine volume measured by 24h urine collection

Nature and extent of the burden and risks associated with participation, benefit and group relatedness:

- BIS and blood pressure measurements will be achieved by non-invasive techniques which pose a minimal burden to the patient.
- Blood sampling will as much as possible coincide with regular blood samplings for clinical purposes. The risk of venipuncture-related complications is considered moderate when performed in the non-dominant arm, as this can influence negatively on a future vascular access.
- All subjects undergo echocardiography. Analysis of the echocardiography will be done during follow-up period. Aberrant results will be discussed with an expert.
- All study-related costs will not be charged to the patient.

INTRODUCTION AND RATIONALE

Chronic kidney disease (CKD) is defined as abnormalities of kidney structure or function, present for more than 3 months, with implications for health.¹ Classification of CKD is structured according to the estimated glomerular filtration rate of creatinine (eGFR) and albuminuria (Figure 1). CKD is a major health problem and continues to rise globally. Prevalence of CKD is estimated at 11-13% of the adult population, of which 0.1% results in end stage renal disease (ESRD, defined as eGFR < 15ml/min or the need for renal replacement therapy).^{2,3} As well in developed as in developing countries, aging and the higher rate of cardiovascular (CV) events in the general population explains the increase of CKD.² Not only prevalence, but also mortality in CKD population is mainly determined by CV comorbidities.^{4,5} Besides the Framingham classics, novel CV risk factors such as fluid status (FS), malnutrition, inflammation and impaired kidney function itself have gained importance.^{4,6,7}

| | | | Persistent albuminuria categories Description and range | | | | | |
|--|--------|---|--|-----------------------------|--------------------------|--|--|--|
| | | | A1 | A2 | A3 | | | |
| | d Albu | sis of CKD by GFR uminuria Categories: KDIGO 2012 | Normal to mildly increased | Moderately increased | Severely increased | | | |

Based on the above mentioned associations between risk factors and outcome in the CKD population, the question rises what specific hemodynamic profile (including FS and BP) is associated with a severe CV comorbidity cascade leading towards more CV events, hospitalizations, rapid decline of kidney function and acceleration of the initiation of renal replacement therapy.

Assessment of the hemodynamic profile, cardiac- and kidney function in predialysis patients

During progression to ESRD, accumulation of fluid occurs silently. Clinical assessment of FS is not straightforward in CKD patients. While prevalence of overhydration in CKD stages 3 - 5 is estimated at 50%,^{6,25,26} 20% of these patients is non-edematous at clinical examination.⁶ The gold standard to measure fluid distribution in the human body is dilution of deuterium and sodium bromide solution for extracellular water (ECW) and total body potassium for intracellular water (ICW). However, these techniques are invasive and not applicable in routine clinical practice. **Bioimpedance spectroscopy** (BIS) is a noninvasive and easy-to-use technology in fluid assessment. Some BIS instruments have been validated in hemodialysis patients against dilution methods.²⁷⁻³⁰ BIS provides the possibility to estimate total body water (TBW), extracellular volume (ECV), intracellular volume (ICV), fat-free mass, fat mass and muscle mass.^{31,32} Also, blood volumes can be accurately estimated by BIS and can optimize BP treatment.³³

In contrast to the hemodialysis population, the clinical use of BIS in fluid management of non-dialysis CKD stages 3 - 5 is less frequently implemented. Observational research has shown that BIS identifies FO in 20% of non-edematous patients with CKD stages 3 - 5, and showed impairment of body composition in absence of overt signs of malnutrition.^{6,25} BIS-derived parameters as FO or lean tissue mass are associated with more rapid decline in residual renal function (RRF), higher CV morbidity and mortality compared to euvolemic CKD-patients.^{9,10,26}

The combination of electrocardiography (ECG) and echocardiography is the easiest and cheapest reliable method to evaluate LVH. However, the gold standard is magnetic resonance imaging (MRI), this is not widely used because of individual MRI tolerance and costs.

Clinical evaluation of kidney function decline is currently performed by longitudinal follow up of serum creatinine concentration and eGFR of creatinine (expressed by the eGFR CKD-EPI equitation), and albuminuria.^{1,34} However, due to the variability of creatinine production and tubular secretion, eGFR

12

or creatinine is often precluded from clinical trials. Creatinine clearance [creatinine clearance (*CrCl*) = (urine creatinine concentration x urine volume) / serum creatinine concentration] or mixed creatinine and urea clearance (CrUrCl) improves accuracy.³⁵

Hemodynamic management of CKD progression and CV morbidities in predialysis patients

Prevention of progression to ESRD and CV complications in predialysis patients is currently addressed by targeting the classical risk factors (BP and glycemic control, salt intake and dietary advice, smoking cessation, albuminuria, physical activity). Management of novel CV risk factors like **FS** is not incorporated in the KDIGO CKD guidelines.¹ Furthermore, the recommendation to keep **BP** in CKD patients \leq 140 mmHg systolic and \leq 90 mmHg diastolic because of reduced risk of CV mortality and CV events, is based on office measurements.^{1,36} Home-measured BP is more strongly associated with LVH and is a stronger predictor of CV risk than office BP.³⁷⁻⁴⁰ Also, there is a lack of evidence for the optimal medical management of **heart failure** in ESRD population.¹ The effect of BP control on LVH in CKD patients has not been clearly evaluated yet.^{36,41}

Preservation of **RRF** in hemodialysis patients is associated with prolonged survival and reduction in CV morbidities. Hence, we should move forward in our attempts to preserve renal function and start with innovative interventions in the predialysis period.

Hypothesis

We hypothesize that FO assessed by BIS is associated with a more rapid decline in RRF and that the follow up of the thoracic BIS signal is an equivalent predictor for cardiac function compared to echocardiography. Eventually we hope that our intervention might lead to a better hemodynamic management, deceleration of kidney function decline and reduction of CV morbidity and mortality in CKD population, although this is beyond the scope of this research study.

In order to investigate this hypothesis, we want to perform the HORUZ study. We are interested in the fluid status, BP and thoracic BIS signal of patients with CKD 3 - 5, not on dialysis. We aim to provide more evidence to further support the frequent use of BIS in diagnostic guidelines of patients with CKD.

OBJECTIVES

The primary objective of the HORUZ study is to associate fluid status with kidney function decline in patients with CKD stage 3 (CKD-EPI eGFR 60-30ml/min), 4 (30-15ml/min) and 5 (< 15 ml/min) and compare them to an age- and sex- matched healthy control group. Primary outcome is the mean eGFR decline which will be compared between the FO-group and the non-FO-group.

The secondary objective is to identify the clinical factors associated with FO during a longitudinal follow up. Secondary outcomes of interest are the central volume status (measured by echocardiography and thoracic BIS in combination with photoplethysmography), the cardiac systolic and diastolic function, CV events, hospitalizations, inflammatory- and nutrition status, and quality of life, between CKD stages 3, 4 and 5 and compare them to an age- and sex- matched healthy control group.

STUDY DESIGN

The HORUZ study is a non-randomized trial with intervention of regular BIS- and BP measurements, blood- and urine sampling. Prevalent patients with CKD stages 3, 4 and 5 and an age- and sex- matched healthy control group will be included. Inclusion period will last 18 months and CKD-patients will be followed up for 12 months.

STUDY POPULATION

1. Population

206 patients with CKD stages 3-5 will be included from the outpatient clinic of Ziekenhuis Zuid-Oost Limburg in Genk (Belgium).

A healthy control group for the cross-sectional part will be recruited through visitors and/or personnel of Ziekenhuis Oost-Limburg in Genk (Belgium).

2. Inclusion criteria

In order to be eligible to participate in this study, a subject must meet the following criteria:

- Prevalent non-dialysis patients with eGFR < 60 ml/min (for CKD subjects)
- Age > 18 years
- Signed informed consent

3. Exclusion criteria

A subject who meets any of the following criteria will be excluded from participation in this study:

- Acute kidney injury
- eGFR < 20ml/min directly post-nephrectomy
- Clinical conditions affecting BIS measurements: limb amputation, impaired skin integrity, brain stimulator, pacemaker with low threshold or unipolar pacemaker.
- Clinical conditions affecting body composition: liver cirrhosis, active infectious disease or any acute CV event (defined as cerebrovascular event, myocard infarction, decompensatio cordis) during the 3 months before screening for inclusion
- Pregnancy

- Not able to sign informed consent

4. Sample size calculation

The primary outcome parameter is the mean eGFR decline which will be compared between the FOgroup and the non-FO-group. We hypothesize that the mean difference between eGFR between these two groups will be 2 μ mol/ml/year. Because the study of Levin et al. does not report a SD, we take the SD of the MDRD study¹: 4.7 μ mol/ml/year^{1,42,43}. In order to show an alpha of 0.05 and a power of 0.8, at least 86 patients would be needed per group. In order to correct for drop-outs, at least 103 patients per group have to be included.

METHODS

1. Study parameters/endpoints

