1.1 Demographic and clinical data

The prevalent CKD stage 3 – 5 population will be screened by the researcher. After verification of the in- and exclusion criteria, eligible patients will be invited to participate the HORUZ study, with approval of their treating nephrologist. After signing the informed consent, data at baseline and during followup visits will be collected on paper clinical report forms (Table 1). Hypertension is defined as an office BP \geq 140/90 mmHg or home BP \geq 130/80 mmHg, or current medication for hypertension.¹ Diabetes mellitus will be assumed to be present in patients who report use of insulin and/or oral hypoglycemic agents. CV diseases include coronary artery disease, as documented by coronary angiography or a history of myocardial infarction, congestive heart failure, cerebrovascular accident, or known peripheral vascular disease. Fluid assessments, including BIS measurements, will be recorded on the HORUZ registration form (Appendix).

The healthy controls included for the cross-sectional analysis will only be followed according to visit 0 and 1.

| | Baseline Visit 0 | Month 1 Visit 1 | Month 3 Visit 2 | Month 6 Visit 3 | Month 9 Visit 4 | Month 12/ end of study Visit 5 |
|--|---------------------|--------------------|--------------------|--------------------|--------------------|-----------------------------------|
| Consent | х | | | | | |
| Demographics: Age (y) Gender Height (cm) Smoking status Etiology CKD Hypertension Diabetes CV disease Tx list | x | | | | | |
| eGFR _{creat} | x | x | x | x | x | x |
| CrUrCl | | x | x | x | x | x |
| 24h urine | | x | x | x | x | x |

Table 1 Schedule of the main data to collect in CKD subjects.

| BP | x | | x | x | x | x |
|-----------------|---|---|---|---|---|---|
| ECG | x | | x | x | x | x |
| Echo cor | | x | | | | x |
| CV events | | x | x | x | x | x |
| Hospitalization | | x | x | x | x | x |
| Medication | x | | x | x | x | x |
| Whole body BIS | x | | x | x | x | x |
| Thoracic BIS | x | | x | x | x | x |
| SF36 | x | | | | | x |
| Adverse event | | x | x | x | x | x |

Abbreviations: BIS, bioimpedance spectroscopy; BP, blood pressure; CKD, chronic kidney failure; Creat, creatinine; CrUrCl, mixed creatinine

and urea clearance; CV, cardiovascular; ECG, electrocardiography; M, month; SF36, short form 36 questionnaire; Tx, transplantation.

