1.3 Secondary endpoints

The secondary objective is to identify the clinical factors associated with FO during a longitudinal follow up. Secondary outcomes of interest are the central volume status (measured by echocardiography and thoracic BIS in combination with photoplethysmography), BP, the cardiac systolic and diastolic function, CV events, hospitalizations, inflammatory- and nutrition status, and quality of life, between CKD stages 3, 4 and 5.

- 1. *Cardiac function:* Electrocardiography and echocardiography (see point 3.3) will be scheduled at baseline, and at 12 months or at end of study visit.
- Thoracic BIS values: a wearable device from Imec Eindhoven will be used to measure thoracic
 BIS values in combination with photoplethysmography and cardiopulmonary index.
- 3. *Blood pressure:* patients will be asked to take BP measurements at home three times a week twice daily with an automatic BP monitor. Mean arterial pressure corrected for heart

frequency will be calculated. BP measurements can be transmitted to the researcher by use of the local Dharma platform.

- 4. *CV events:* CV events defined as hospitalization for coronary disease, heart failure, stroke or peripheral artery disease will be recorded during follow-up.
- 5. *Hospitalization rate and indication:* hospitalization rate and indication will be listed.
- 6. *Inflammatory- and nutrition status:* CRP, ferritin and albumin will be determined every visit (Table 2). Fat tissue mass and lean tissue mass will be analyzed by BIS measurements.
- 7. *Quality of Life assessment:* SF36 questionnaire will be filled in at baseline and end of study visit.

| Table 2 Overview of | f parameters evaluatir | g kidney function, r | enal metabolism a | and inflammation in HORUZ study. |
|---------------------|------------------------|----------------------|-------------------|----------------------------------|

| Assay | Material | Standard care | Frequency |
|-------------------------|--------------|---------------|-------------------|
| Residual renal function | | | |
| Urea | Plasma/serum | yes | Every study visit |
| Creatinine | | | |
| Metabolism and electrol | ytes | | |
| Hemoglobin | Plasma/serum | yes | Every study visit |
| Sodium | | | |
| Potassium | | | |
| Bicarbonate | | | |
| Phosphate | | | |
| Calcium | | | |
| NT-proBNP | | No | Every study visit |
| Inflammation | | | |
| C-reactive protein | Plasma/serum | yes | Every study visit |
| Leucocytes | | | |
| Albumin | | | |

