2.3 Suspected unexpected serious adverse reactions (SUSAR)

Not applicable.

3. Follow-up of adverse events

AE according to the study are considered very unlikely, due to the fact that only non-invasive methods are used. All AEs will be followed until a stable situation has been reached and treated to standard procedures.

4. Data Safety Monitoring Board (DSMB)

Not applicable.

STATISTICAL ANALYSIS

A table with baseline characteristics of all subjects will be provided. Baseline characteristics of the population will be expressed as the mean \pm standard deviation if normally distributed, or as the median [25th – 75th percentile] as not normally distributed, for continuous and dichotomous data, and as the frequency (%) for categorical data. Measurements of drop-outs will be included until the moment of withdrawal from the study. Normality in distribution will be tested by the Shapiro-Wilk statistic. Repeated measurements ANOVA techniques will be used for analysis. Pearson's Chi-squared test will be used to assess whether there is any distinction between subgroups in rate of kidney function decline. In case the analysis of the baseline characteristics showed any clinically relevant imbalance, we will also perform a multivariable logistic regression analysis in order to correct for this imbalance. Differences in LVH will be corrected for systolic BP and haemoglobin, as these are predictors of LVH in predialysis population.¹⁵ Depending on the level of measurement a Chi-squared test or a T-test will be used to assess differences in secondary study parameters, and logistic and linear regression for baseline-corrected estimates. Tests will be considered significant if p-values are ≤ 0.05 .

ETHICAL CONSIDERATIONS

1. Regulation statement

The study will be conducted according to the principles of the Declaration of Helsinki (Fortaleza, Brasil, 2013).

2. Recruitment and consent

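### Secondary contrasts between CKD stages and with healthy controls rest on unpaired tests, with no commitment to adjust for age and sex and no stated matching target

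*Combined protocol and SAP*

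**What the plan says.** **Contrasts.** The Summary and OBJECTIVES plan to compare secondary outcomes "between CKD stages 3, 4 and 5 and compare them to an age- and sex- matched healthy control group". METHODS 1.3 repeats the between-stage comparison but does not mention controls.

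**Controls.** STUDY DESIGN says: "Prevalent patients with CKD stages 3, 4 and 5 and an age- and sex- matched healthy control group will be included". STUDY POPULATION 1 adds: "A healthy control group for the cross-sectional part will be recruited through visitors and/or personnel". METHODS 1.1 limits their participation: "The healthy controls included for the cross-sectional analysis will only be followed according to visit 0 and 1". No section gives the number of controls, the ratio, the calliper, or whether matching is to the whole cohort, to each stage or to individuals.

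**Analysis.** STATISTICAL ANALYSIS says: "Depending on the level of measurement a Chi-squared test or a T-test will be used to assess differences in secondary study parameters". The same sentence continues with "logistic and linear regression for baseline-corrected estimates", without defining the term. An earlier sentence adds a multivariable logistic model if baseline characteristics show an imbalance of clinical relevance. The only covariates named anywhere are systolic BP and haemoglobin, and only for LVH. No paired or stratified analysis is described.

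**Body composition.** METHODS 1.3 says: "Fat tissue mass and lean tissue mass will be analyzed by BIS measurements". LTI is in the abbreviation list, and Table 1 collects height, age and gender at visit 0.

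**The concern.** The sponsor matches on age and sex, and so treats them as potential confounders, but the named tests then leave them out. Two problems could follow.

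- **Bias.** Unless controls are matched within each stage, one control group need not resemble stage 3, 4 or 5 taken singly. The stages are not matched to each other at all. For any outcome related to age or sex, part of an unadjusted difference could then reflect who is in each group.
- **Precision.** An unpaired test against matched controls does not use the precision that matching provides.

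The documents give reasons to expect that age and sex matter. Stage is defined by CKD-EPI eGFR, whose formula (METHODS 1.2) contains both. The Summary lists gender as a determinant of the BIS signal. The LVH cut-offs in METHODS 3.3 differ by sex.

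**Working it through.** **The plan's own figure.** The only sample-size figure is for the primary comparison: difference 2, SD 4.7, alpha 0.05, power 0.80. n = 2 × (1.960 + 0.842)² × 4.7² / 2² = 86.7 per group, so 87 against the stated 86 (power at 86: 79.7%). It reproduces, but it says nothing about the stage or control contrasts, for which no size is given.

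**Does stage depend on age by construction?** At equal creatinine, 20 more years multiplies CKD-EPI eGFR by 0.993^20 = 0.87, a fall of about 13%. This makes age differences between stages plausible. It does not show that they exist.

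**Assumed inputs for size.** The 206 patients are split 69/69/68 across stages 3/4/5, with one control per patient matched exactly on age to the whole cohort. Outcome and age each have SD 1 within a stage. Age explains R² = 10% or 30% of outcome variance. There is no true group difference. Each scenario had 2,000 simulated trials. Sex was not simulated; it would act in the same way. The outcome is continuous.

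**Bias of the unadjusted T-test.** Bias = √R² × gap in mean age (in SD). For a gap of 0.25: 0.316 × 0.25 = 0.08 and 0.548 × 0.25 = 0.14. For a gap of 0.5: 0.16 and 0.27. In the third scenario below, the pooled mean age is (69×0 + 69×0.3 − 68×0.5)/206 = −0.065, so stage 5 differs from controls by −0.435 and the bias is −0.14 and −0.24. The simulation agrees:

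| Mean age of stages 3/4/5 (SD) | Contrast | Bias in SD (R² 10%; 30%) | False-positive rate (10%; 30%) |
|---|---|---|---|
| 0 / 0 / 0 | 5 v controls | 0.00; 0.00 | 5.0%; 3.5% |
| 0 / 0 / 0 | 5 v 3 | 0.00; 0.00 | 5.0%; 5.6% |
| −0.25 / 0 / +0.25 | 5 v controls | 0.07; 0.14 | 6.8%; 14.5% |
| −0.25 / 0 / +0.25 | 5 v 3 | 0.15; 0.27 | 14.0%; 35.2% |
| 0 / +0.3 / −0.5 | 5 v controls | −0.14; −0.24 | 15.1%; 38.9% |
| 0 / +0.3 / −0.5 | 5 v 3 | −0.15; −0.28 | 12.8%; 38.0% |

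**Standard error of the unpaired test, relative to the true SD of the estimate.**
- Whole cohort v matched controls: 1/√(1−R²) = 1.05 and 1.20 by formula; 1.04 to 1.20 simulated.
- One stage v controls matched to the whole cohort: 1.00 to 1.11.
- One stage v its own matched controls: 1.04 to 1.21. Bias is then at most 0.012 SD and the false-positive rate is 1.5% to 4.3%, so the test is unbiased but conservative.
- Stage v stage: 0.99 to 1.04, so valid.

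**With age in the model** (stage 5 v controls and v stage 3): bias at most 0.01 SD, standard-error ratio 0.98 to 1.02, false-positive rate 4.3% to 5.7%. For stage 5 v stage 3 with equal ages, the SD of the estimate falls from 0.172 to 0.143 at R² = 30%, and from 0.171 to 0.163 at 10%. Where ages differ and R² is 10%, there is practically no precision gain (0.168 v 0.169); the benefit there is removal of bias.

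**The case against.** The strongest reply is that the plan is silent, not wrong. It has several parts.

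- **Matching target.** A reader might infer that controls are matched to the cohort as a whole. The documents do not say so. Matching to each stage or patient by patient fits the text equally well, and would largely remove age and sex imbalance between a stage and its own controls. This stands. It does not help the stage-versus-stage contrasts.
- **Adjustment.** A reader might infer a wholly unadjusted plan. That is too strong: regression is in the same sentence as the tests, and correction for baseline characteristics, including age and sex, is a possible reading. But the term is undefined and age and sex are not named. If it means correction for an outcome's baseline value, it cannot apply to a cross-sectional comparison.
- **Imbalance clause.** One might argue that matching would hide imbalance and the clause would never apply. The text does not restrict the check to pooled groups, so a by-stage baseline table could trigger it. Even then it sets no threshold and offers only a logistic model.
- **Standard errors.** The claim that they are too wide throughout fails, because stage-versus-stage groups are unmatched and the T-test is valid there. Figures of 12% to 29% from 1/√(1−R²) at an assumed R² of 20% to 40% measure precision forgone, not a miscalibrated test.
- **Body size.** LV mass is already indexed (LVMI), and the text does not say that absolute lean and fat mass are the analysis variables. Only a suggestion remains.

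**Conclusion.** The point holds in a limited form. The named tests for the stage and control contrasts use neither the matching nor age and sex, the added regression wording does not commit to either, and the matching target is missing. The contrasts may be confounded. The documents do not show that they are, because that requires age or sex to differ between the groups compared and to relate to the outcome, and no figures are given on either.

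Under the assumed inputs, bias runs from nil (equal stage ages) to about 0.24 SD for stage 5 v controls and 0.28 SD for stage 5 v stage 3, with false-positive rates up to about 39%. Unpaired standard errors are conservative only against matched controls, by up to about 1.2 times. Only secondary outcomes are concerned; the primary comparison of fluid-overloaded with non-overloaded patients is not affected. The change is still worth making, because an adjusted model is a better method than the named tests for non-randomised groups and needs no new data.

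**What to change.** 1. Make the main analysis of every stage-versus-stage and stage-versus-control contrast a linear model (continuous outcomes) or logistic model (binary outcomes) with group, age and sex. Keep the unadjusted tests as descriptive.
2. State the matching target (whole cohort, each stage or individual), the ratio and the age tolerance. If pairs or strata are formed, reflect them by a paired analysis or by including the matching factors.
3. Define the baseline-corrected regression by naming its covariates, and present baseline characteristics by stage and for controls.
4. As a secondary suggestion, report lean and fat tissue per height squared.

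The cost is a few lines in the statistical section and in the description of the controls. Age, sex and height are already collected at visit 0, which controls attend.

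The precision figures above are for continuous outcomes and should not be carried over to odds ratios.
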